### 11. SECONDARY AIMS

The **secondary aims** are to determine the effectiveness of HWC in improving

1. Overall cardiovascular disease (including stroke) risk at 6 months post-randomisation based on the LS7 compared to Baseline

2. Individual LS7 behavioural risk factors at 3-, 6- 9- and 12- months post-randomisation compared to Baseline
3. Awareness about stroke symptoms, risk factors and their management 6- and 12- months post-randomisation compared to Baseline
4. Quality of life, at 6- and 12- months post-randomisation compared to Baseline
5. Cognitive outcomes at 6-, and 12- months post-randomisation compared to Baseline
6. Mood outcomes compared to Baseline
7. Adherence to CVD medications at 3, 6-, and 9 and 12- months compared to Baseline
8. CVD/adverse outcomes at 12 months post randomisation.
9. Health and service costs at 12 months post randomisation
10. Productivity status at 12 months post randomisation

Secondary outcomes are:

1. systolic blood pressure, total cholesterol, blood glucose at 6-months post randomisation
2. change in proportion of participants in 'high' and 'intermediate' to 'low' risk on LS7 at 6-months post randomisation
3. Stroke risk from Stroke Riskometer – 5- year absolute and relative risk at 6- and 12-months post randomisation
4. Quality of life (EQ5D) at 6-months post randomisation
5. Stroke awareness at 6- and 12-months post randomisation
6. Cognitive assessment score (Montreal Cognitive Assessment)
7. Medication adherence (Self-Efficacy For Appropriate Medication Use Scale (SEAMS))
8. CVD adverse outcomes (fatal and nonfatal stroke, TIA, myocardial infarction and heart failure, death attributable to CVD and all-cause mortality)
9. Healthcare and community service costs assessed as self-reported service use questionnaire at follow up. Productivity status will be self-reported and will include items regarding status (e.g., paid work, voluntary work, homemaker, student, unemployed), hours (e.g., full/part time), compared to hospitalisation pre-stroke status.

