### 34. INFERENCE ANALYSES

Intention to treat (ITT)[95] analyses and per protocol analysis will be used. To address the primary hypothesis ANCOVA will be used to compare the difference in systolic blood pressure at 6-months post randomisation between the HWC and usual care groups, accounting for baseline stratification factors: (age, gender and ethnicity), referral centres, geographical region and known influential clinical characteristics (e.g., comorbidities). To address the secondary hypotheses linear mixed effects (LME) repeated measures models will be used to investigate the differences in (1) adherence to medication (2) health-related quality of life (3) incidence of new vascular events including death (4) life satisfaction (5) cognition (6) mood) and (7) health service utilisation costs between the HWC and Usual care groups, and by ethnicity (sub-group analysis) at 6-months (plus

life-style and adherence at 1-year post-randomisation. These LMEs will model effect of time (baseline, 3-, 6- 9- and 12-months (medication adherence, lifestyle and awareness at only 12 months), post-randomisation whilst accounting for key demographic stratification factors known to confound with outcomes. Any data not collected within 6-weeks of the follow-up points will be classified as missing data. Baseline covariates of age, sex, most recent blood pressure measure and any additional variables predictive of outcome data will be included in the imputation model.[46] The reasons for missingness and the reasons will be recorded and accounted for. Sensitivity analyses will be conducted to test the assumptions of the model (including a complete case analysis in which only subjects with complete data are included). Familywise error control will be used to account for the multiplicity of tests. Inferences will be based on a 5% significance level and two-sided alternatives.

For the analysis of - CVD adverse outcomes (fatal and nonfatal stroke, TIA, myocardial infarction and heart failure, death attributable to CVD and all-cause mortality), we will use Kaplan-Meier life-test and estimate the hazard ratios (HR) and adjusted HR using time-to-event Cox regression analysis. Time to event analysis will include recurrent events and time-dependant variables where appropriate.

Competing risk method will also be applied to compare the CVD adverse outcomes between the two interventional groups, accounting for mortality outcome.

---

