### Section 10: Current Medications.

10.2. CVD Medications prescribed at discharge (Tick all that apply)

- Aspirin  
 Dipyridamole  
 Clopidogrel  
 Warfarin  
 Dabigatran  
 Rivaroxaban  
 Blood pressure lowering medication(s)  
 Lipid lowering therapy (statins)  
 Diabetes medication(s),  
 Mood modification therapy  
 Oral contraceptives  
 Supplements (herbal or vitamins)  
 Other  
 None of the above  
 (Complete Section 11 only if medications medications are taken (Q10.1))

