### Section 11: Self-Efficacy For Appropriate Medication Use Scale [SEAMS]

**How confident are you that you can take your medications correctly:**

	Not At All Confident	Somewhat Confident	Very Confident
11.1. When you take several different medicines each day?			
11.2 When you are away from home?			
11.3 When no one reminds you to take the medicine?			
11.4 When you take medicines more than once a day?			

- 11.5 When the schedule to take the medicine is not convenient?
- 11.6 When your normal routine gets messed up?
- 11.7 When you get a refill of your old medicines and some of the pills look different than usual?
- 11.8 When you are not sure how to take the medicine?
- 11.9 When you are not sure what time of the day to take your medicine?
- 11.10 When a doctor changes your medicines?
- 11.11 When they cause some side effects?
- 11.12 When you are feeling sick (like having a cold or the flu)?

---

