11.14 Do you have trouble remembering to take your medication?  Yes  No

---

11.15 How often do you have difficulty remembering to take all your medication?  Never/Rarely  Once in a while  
 Sometimes  Usually  
 All the time

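### The follow-up form makes the adherence items conditional on medicines being taken, citing an unprinted question, so a participant who has stopped everything can have no adherence value at that visit

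*Protocol*

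**What the plan says.** Section 11 of the protocol (Secondary aims) includes "Adherence to CVD medications at 3, 6-, and 9 and 12- months compared to Baseline", and its list of secondary outcomes names the instrument: "Medication adherence (Self-Efficacy For Appropriate Medication Use Scale (SEAMS". Section 34 states that "linear mixed effects (LME) repeated measures models will be used to investigate the differences in (1) adherence to medication", among other outcomes, between coaching and usual care.

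The data come from Appendix C. Form B (baseline) and Form F (3, 6, 9 and 12 months) both have a Section 10 headed as current medications. Its only printed item is "10.2. CVD Medications prescribed at discharge (Tick all that apply". The list under it ends with a none-of-the-above option, followed by the instruction "Complete Section 11 only if medications medications are taken (Q10.1". The wording is the same on both forms.

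Section 11 of each form then holds the twelve SEAMS items, the last being "11.12 When you are feeling sick (like having a cold or the flu", the SEAMS total (11.13), and two further items, the first of which is "11.14 Do you have trouble remembering to take your medication". All of them fall under the same instruction.

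**The concern.** An adherence outcome should be obtained from everyone who has been prescribed treatment, above all from those who no longer take it. As worded, the instruction does the opposite for one group: a participant who was prescribed medicines at discharge and takes none by, say, month 6 is not asked Section 11. That participant is the clearest adherence failure, yet has no adherence value at that visit.

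The skip is decided after randomisation, by a behaviour the intervention is expected to change. The protocol's background section on health and wellness coaching cites improved medication adherence among people who are coached. If coaching prevents complete stopping, usual care loses more of its poor values than the coached arm does, and part of any benefit disappears from the comparison.

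The gap is also hard to repair afterwards. Item 10.2 asks about discharge prescriptions even at month 12, so a ticked 10.2 with a blank Section 11 could mean that everything was stopped or that the section was simply not completed.

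**Working it through.** **Reading the forms.** The plan states no figure on this point, so there is none to reproduce. The check is mainly of the text.

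1. The condition is that medicines are taken, in the present tense, under a heading about current medications. That points to current use.
2. The condition refers to item 10.1. Section 10 as printed starts at 10.2 on both forms, so the item that should define the condition is not there.
3. The only printed item concerns prescription at discharge, which is fixed before randomisation. That points to prescription, not use.
4. All SEAMS items, the total, and items 11.14 and 11.15 sit behind the condition. No other printed item on Form F records that a medicine was stopped, and no text says how such a participant is scored.
5. At baseline (Form B) the skip precedes randomisation and cannot depend on arm. The problem lies in Form F.

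Points 1 and 3 lead staff to different actions for the same participant. Under 1 the total stopper is skipped; under 3 the total stopper is asked.

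**Illustration of size.** Every input except the number followed up is an assumption, because the documents give no stopping rate, no SEAMS standard deviation and no SEAMS score for people who have stopped.

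- Followed up per arm: 180 × (1 − 0.20) = 144, from the planned allocation and the assumed 20% loss.
- Proportion stopping everything in usual care, p_U: 2% to 20% (assumed).
- Proportion in the coached arm, p_H: 0.25 to 1.0 times p_U (assumed).
- Gap g by which stoppers would score below takers: 6 to 12 points (assumed). The printed form has 12 items scored 1 to 3, a range of 12 to 36.
- Takers have the same mean in both arms (assumed).

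Difference among all prescribed = (p_U − p_H) × g. Difference among takers only = 0.

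| p_U | p_H | g = 6 | g = 12 | Takers only |
|---|---|---|---|---|
| 5% | 2.5% | 0.15 | 0.30 | 0 |
| 10% | 5% | 0.30 | 0.60 | 0 |
| 20% | 5% | 0.90 | 1.80 | 0 |
| 10% | 10% | 0 | 0 | 0 |

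Participants with no value at the visit: 144 × 0.02 ≈ 3 to 144 × 0.20 ≈ 29 in usual care, and about 1 to 29 in the coached arm.

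With equal stopping the contrast is not shifted in this model, but each arm's mean is overstated by p × g. At 10% that is 0.10 × 6 = 0.6 to 0.10 × 12 = 1.2 points.

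For scale, assume also a standard deviation of 4 among takers. Stoppers widen the spread, so the variance per arm is 16 + p(1 − p)g². For 10% against 5% with g = 12 this gives 16 + 0.09 × 144 = 28.96 and 16 + 0.0475 × 144 = 22.84. The standard error is √((28.96 + 22.84)/144) = 0.60, so the lost 0.60 points is about 1.0 standard error. With g = 6 the variances are 19.24 and 17.71, the standard error is √(36.95/144) = 0.51, and the lost 0.30 points is about 0.6 standard errors.

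**The case against.** The strongest reply is that the instruction was probably meant to say: skip Section 11 if none of the listed medicines was prescribed. It stands directly under a prescription list that ends in a none-of-the-above option. On that reading stoppers are still asked, and the skip is fixed before randomisation. This is plausible, and it means the documents do not establish that stoppers will be excluded. It does not remove the point: the printed words refer to taking, the item they cite is absent, and under either reading no printed item records stopping.

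Other limits also stand:

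- The condition covers medicines of any kind, and the list includes supplements, oral contraceptives and an open category. Only someone taking nothing at all is skipped. Someone who has stopped every cardiovascular medicine but still takes something else is asked, as is every partial non-adherer.
- SEAMS measures confidence in taking medicines correctly. Nothing in the protocol says that a person who has stopped would score low on it.
- A reader might infer that these participants leave the endpoint altogether. They do not: the repeated-measures model keeps their other visits and draws on their own earlier scores. What it cannot do is recover the unmeasured value, which it predicts from people and visits where medicines were being taken.
- Section 34 promises that reasons for missing data will be recorded and accounted for, and the section on case report forms requires missing data to be explained. That helps only if staff treat a section skipped on instruction as missing. How stoppers are scored may properly be left to a statistical analysis plan, but no such plan can supply information the form never collected.

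**Conclusion.** The point holds as a defect of the forms. The rule deciding who is asked the adherence items is worded in terms of taking medicines, cites an item that is not printed, and sits beside an item about prescription. Applied literally, it makes measurement of a secondary endpoint depend on post-randomisation behaviour that is itself the outcome.

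If coaching reduces complete stopping, the bias is towards no effect. If stopping is equal, the contrast is roughly unbiased and adherence is overstated in both arms. The lost difference of 0 to 1.8 points rests wholly on the assumed stopping rates, the assumed gap and equal means among takers, and shows scale only.

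A reader might go further and conclude that the endpoint is known to be biased by a stated number of standard errors, or that every stopped medicine is non-adherence. The documents support neither: they give no stopping rate and no SEAMS spread, and a medicine may have been discontinued by the prescriber. The primary systolic blood pressure endpoint and the sample size are unaffected.

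**What to change.** 1. On Forms B and F, reconcile the instruction with the printed items: either print the missing item 10.1 or remove the reference, and make Section 11 conditional on any medicine having been prescribed, not on medicines being taken.
2. On Form F, add an item on current status that separates still taking, stopped by the participant and stopped by the prescriber.
3. State that participant-initiated stopping is reported as non-adherence by arm alongside SEAMS, and is not converted into an assigned SEAMS score. Prescriber-led discontinuation is kept apart and not counted as non-adherence.

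The cost is one branching condition in REDCap and one or two extra tick boxes, with no added visits. A few participants will answer confidence items about medicines they have stopped. The change is needed before follow-up data accrue, because a skipped section cannot be reconstructed later.

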### Section 11: Self-Efficacy For Appropriate Medication Use Scale [SEAMS]

**How confident are you that you can take your medications correctly:**

	Not At All Confident	Somewhat Confident	Very Confident
11.1. When you take several different medicines each day?			
11.2 When you are away from home?			
11.3 When no one reminds you to take the medicine?			
11.4 When you take medicines more than once a day?			

- 11.5 When the schedule to take the medicine is not convenient?
- 11.6 When your normal routine gets messed up?
- 11.7 When you get a refill of your old medicines and some of the pills look different than usual?
- 11.8 When you are not sure how to take the medicine?
- 11.9 When you are not sure what time of the day to take your medicine?
- 11.10 When a doctor changes your medicines?
- 11.11 When they cause some side effects?
- 11.12 When you are feeling sick (like having a cold or the flu)?

---

11.13 SEAMS Score Total \_\_\_\_\_

---

11.14 Do you have trouble remembering to take your medication?  Yes  No

---

11.15 How often do you have difficulty remembering to take all your medication?  Never/Rarely  Once in a while  
 Sometimes  Usually  
 All the time

## 12. EQ-5D - 5L

**Under each heading, please tick the ONE box that best describes your health TODAY**

12.1. Mobility  I have no problems in walking about  
 I have slight problems in walking about  
 I have moderate problems in walking about  
 I have severe problems in walking about  
 I am unable to walk about

---

12.2. Self-Care  I have no problems washing or dressing myself  
 I have slight problems washing or dressing myself  
 I have moderate problems washing or dressing myself  
 I have severe problems washing or dressing myself  
 I am unable to wash or dress myself

---

12.3. Usual Activities (e.g. work, study, housework, family or leisure activities)  I have no problems doing my usual activities  
 I have slight problems doing my usual activities  
 I have moderate problems doing my usual activities  
 I have severe problems doing my usual activities  
 I am unable to do my usual activities

---

12.4. Pain/Discomfort

- I have no pain or discomfort
- I have slight pain or discomfort
- I have moderate pain or discomfort
- I have severe pain or discomfort
- I have extreme pain or discomfort

---

12.5. Anxiety/Depression

- I am not anxious or depressed
- I am slightly anxious or depressed
- I am moderately anxious or depressed
- I am severely anxious or depressed
- I am extremely anxious or depressed

---

12.6. EQ VAS - Health State Score

(We would like to know how good or bad your health is TODAY. 100 means the best health you can imagine. 0 means the worst health you can imagine.)

---

12.7. Any comments.

---

---

### Section 13: Risk Factor Awareness

---

13.1. Which of the following best describes a stroke?  
(please tick one or more boxes)

- A heart attack
- A brain attack
- When blood supply to the brain is stopped or blocked
- Not sure, but has something to do with the brain
- Not sure, but it is like a heart attack
- Don't know

---

13.2. What may be signs that someone is having a stroke? (please tick one or more boxes)

- Chest pain
- Rash
- Drooping face
- Coughing
- Slurred speech
- Not able to lift one or both arms
- Stress

---

13.3. What causes you to be at higher risk of stroke?  
(please tick one or more boxes)

[figure not shown]
- High blood pressure
- High cholesterol
- Diabetes
- Smoking
- Asthma
- Being tired
- Family history of stroke
- Excessive alcohol intake
- Stress
- Poor diet
- Being overweight (obesity)
- Lack of exercise/fitness
- Irregular heart beat

**13.4. What is the most important thing to do if you or someone else experiences any of the following?**

[figure not shown]
	Advise them to rest	Contact a doctor	Call a family member	Call an ambulance	Go to the hospital	Do nothing
13.4.1. Paralysis or weakness of the face						
13.4.2. Not able to lift one or both arms, or one arm paralysed						
13.4.3. Slurred speech, or unable to understand what someone else is saying						

**Section 14: Life Satisfaction**

14.1. On a scale of 1 to 10 indicate where you stand right now. (Note: 10 represents the best possible life and the 1 represents the worst possible life.)

14.2. On a scale of 1 to 10 indicate where in the ladder you stand right now. (Note: 10 represents the best level of satisfaction with your life and 1 represents the worst level of satisfaction.)

**13.3. Satisfaction with Life Scale**

**Below are five statements with which you may agree or disagree. Using the scale below, indicate your agreement with each item by checking the appropriate radio button preceding that item. Please be open and honest in your response.**

	Strongly Disagree	Disagree	Slightly Disagree	Neither Agree or Disagree	Slightly Agree	Agree	Strongly Agree
In most ways my life is close to my ideal.							
The conditions of my life are excellent.							
I am satisfied with life.							
So far I have gotten the important things I want in life.							
If I could live my life over, I would change almost nothing.							

14.3.1 Satisfaction with life total score

---

**Section 15. LS7 Questionnaire****Part A: Blood Pressure**

15A.1. Systolic blood pressure (mm Hg) Reading 1

---

15A.2. Diastolic blood pressure (mm Hg) Reading 1

---

15A.3. Systolic blood pressure (mm Hg) Reading 2

---

15A.4. Diastolic blood pressure (mm Hg) Reading 2

---

15A.5. Systolic blood pressure (mm Hg) Reading 3

---

15A.6. Diastolic blood pressure (mm Hg) Reading 3

---

15A.7. Average Systolic blood pressure (mm Hg)

---

If the average systolic blood pressure is less than 130, please stop here. Participant is not eligible.

15A.8. Average Diastolic blood pressure (mm Hg)

---

15A.9. LS7 BP Score

---

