## 18. ASSESSMENTS

There will be a total of five assessments: baseline, 3, 6, 9 and 12 months. Eligible participants will be contacted by CRAs to book appointments for assessments. The baseline and 6-month assessments will be conducted face to face to allow the measurement of the primary outcome metrics for the LS7 (height, weight, blood pressure, blood glucose and blood cholesterol) as well as cognitive assessments. The 3-, 9- and 12-months assessments will be conducted over telephone, at a suitable time.

For face-to-face assessments, the participant will have the option of attending a clinic at one of the three locations at the AUT campuses (AUT North, City or South). Participants travelling to clinics will be provided a petrol or supermarket voucher (NZ \$20) for parking or travel costs.

Participants who are unable to travel to clinic sites will be offered a home visit to conduct the baseline and 6-month assessments.

---

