## ASSESSMENT INFORMATION

The Primary Outcome measure of **blood pressure** will be collected as part of the LS7 questionnaire. The LS7 is a simple scoring system to assess cardiovascular health with scores ranging from 0 to 14, with the overall LS7 score categorised as inadequate (0–4), average (5–9), or optimum (10–14) cardiovascular health. These are; blood pressure, cholesterol, glucose, body mass index, smoking, physical activity, and diet.[37] The total LS7 score as well as individual LS7 items apart from blood pressure are secondary outcomes.

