## 29. OUTCOME ASSESSMENTS (SEE TABLE 1 FOR THE FULL LIST OF OUTCOMES)

**Baseline:** The baseline assessment will be conducted prior to randomisation, and within 6 weeks of the index event. The Baseline assessment will be conducted in-person. The initial part of the assessment will be used to determine the full eligibility of the participant for the TIIPS trial. The full assessment will be completed for eligible participants only, and will include all measures required to analyse the primary and secondary outcomes

**3 months** (plus or minus 2 weeks from date of randomisation): The assessment will be conducted by telephone only, and will assess secondary outcomes.

**6 months** (primary outcome) (plus or minus 2 weeks from date of randomisation): The 6- month assessment be conducted in-person and will re-assess the primary outcome as well as secondary outcomes.

**9 months** (plus or minus 2 weeks from date of randomisation): The assessment will be conducted by telephone only, and will assess secondary outcomes.

**12 months** (plus or minus 2 weeks from date of randomisation): The assessment will be conducted by telephone only, and will assess secondary outcomes.

---

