## 30. PRIMARY END POINTS

The primary end-point will be measured at 6 months post randomisation. The primary end-point will be the difference in the mean change in systolic blood pressure at 6 months post-randomisation between UC and HWC.

---

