# APPENDICES

## 38. APPENDIX A: PHYSICAL MEASURES AND EQUIPMENT

### *Requirements for face-to-face visit*

The Participant File with information and consent form.

MoCA hardcopy for cognitive screening.

Tablet or laptop within REDcap database open to 'baseline assessment – physical measurements' (can be used offline if no internet)

Completion of questionnaires in REDCap.

Reminder sheet about blinding of the Research Assistants so that participants do not disclose if they are in the HWC group.

The following will occur at each visit:

Any questions regarding the information sheet or consent form will be addressed, ensuring that the participant received an electronic copy of the consent form to keep and reassured that they can withdraw at any time.

Before the baseline assessment the Research Assistant should review the completed online questionnaires. This will confirm eligibility in terms of medical history before completing further eligibility checks.

The first eligibility check will be the physical measurement of blood pressure (See below under PHYSICAL MEASUREMENTS). If participants have met this criterion, the assessment will continue. The clinical testing will confirm how many biomedical items are in the unhealthy range.

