## 40. APPENDIX C CASE RECORD FORMS

### List of TIIPS study case record forms

	Form Name	Purpose
1	Form A NHI number	Confidential record of NHI number
2	Form B Baseline and Screening	Screening for eligibility, and Baseline demographic and health related information
3	Form C Contact Details	Record of participant contact details, alternate contact and GP contact
4	Form F Follow-up	Follow-up assessments at 3, 6, 9 and 12 months
5	Form R Randomisation	Completion of data entry for randomisation, and record of group allocation
6	Form S Serious adverse events	Record of stroke/TIA/MI recurrent events, death and hospitalisation
7	Form Z Coaching assessment and compliance	Record of coaching sessions, compliance, and assessment of coaching quality

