7.1.8. MoCA total score

(If MOCA  $\leq$  25, the participant is not eligible for the study.)

Cognitive Impairment WARNING !!!!

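### The follow-up form repeats the screening stop at systolic BP below 130, so secondary-outcome data at the 6-month visit would go missing according to the primary outcome

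*Protocol*

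**What the plan says.** The Appendix C list describes Form F as "Follow-up assessments at 3, 6, 9 and 12 months", and its visit tick-box offers only those four visits, so every use is after randomisation. In its Section 15 Part A, after three pairs of readings and the average systolic value, item 15A.7 carries the instruction "If the average systolic blood pressure is less than 130, please stop here. Participant is not eligible". Form B has the same words in the same place. There they serve a purpose: Appendix A says of the baseline visit that "The first eligibility check will be the physical measurement of blood pressure".

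Form F item 7.1.8 also keeps a note that with a MoCA of 25 or less "the participant is not eligible for the study". Form B follows that note with a command to stop. Form F keeps the warning but drops the command.

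The Assessment Information section says that the primary outcome, blood pressure, "will be collected as part of the LS7 questionnaire", which is this part of the form. Section 30 defines the endpoint: "The primary end-point will be the difference in the mean change in systolic blood pressure at 6 months post-randomisation between UC and HWC". Section 29 says of the visit concerned: "The 6- month assessment be conducted in-person and will re-assess the primary outcome as well as secondary outcomes". Section 18 says: "The 3-, 9- and 12-months assessments will be conducted over telephone, at a suitable time". Blood pressure is therefore measured after randomisation only at 6 months.

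**The concern.** Eligibility is settled before randomisation and cannot be decided again on a follow-up value. On Form B the line screens people out. On Form F it acts on people already in the trial, and on the variable that the intervention is meant to lower. Because Form B admits only those at 130 or above, anyone caught at 6 months has fallen below the entry threshold.

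At stake first are the secondary endpoints in section 31 that are recorded after item 15A.7: the LS7 total, the individual lifestyle components, and health service use. If the instruction is followed, their missingness is fixed by the 6-month systolic value and differs by arm whenever the arms differ in systolic BP. The height, weight and capillary blood measurements cannot be taken retrospectively for that visit.

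**Working it through.** **Step 1: what lies before and after the stop.**

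| Position on Form F | Items |
|---|---|
| Before the stop | MoCA, HADS, comorbidities, medications, SEAMS, EQ-5D-5L, awareness, life satisfaction (Sections 7–14); three systolic and three diastolic readings; average SBP (15A.1–15A.7) |
| After the stop | Average DBP and LS7 BP score (15A.8–15A.9); cholesterol, glucose, BMI, smoking, drugs, alcohol, diet, activity, LS7 total (15B–15J); Riskometer (Section 16); health service use (Section 17) |

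The primary value is captured. Average DBP and the LS7 BP score come after the stop, but can be rebuilt from readings and medication data already entered. Everything from cholesterol onward cannot.

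**Step 2: consequence for LS7.** Tables 2 and 3 require SBP below 120 for an ideal BP score of 2. If the stop is obeyed, LS7 totals exist only for SBP of 130 or above, so no recorded 6-month total contains the ideal BP score and none can exceed 14 − 1 = 13.

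**Step 3: how many people.** The Protocol has no figure to reproduce, and the 6-month SBP distribution is not given. Two illustrations follow. Counts use 360 × 0.8 / 2 = 144 per arm, from the sample size and 20% attrition in section 7.

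*Model A (all values assumed except the 6 mm Hg target).* 6-month SBP is normal, usual-care mean μ = 135–145, coached mean μ − 6, SD σ = 16–20. With z = (130 − μ)/σ, the proportion below 130 is Φ(z). The mean of those at or above 130 is μ + σ·φ(z)/(1 − Φ(z)).

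Example with σ = 18:
- Usual care, μ = 140: z = −10/18 = −0.556, proportion 28.9%, mean above the cut 140 + 18 × 0.481 = 148.7.
- Coaching, μ = 134: z = −4/18 = −0.222, proportion 41.2%, mean above the cut 134 + 18 × 0.662 = 145.9.
- Difference among those retained: 2.7 mm Hg, against a true 6.

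| UC / HWC mean, SD | UC below 130 | HWC below 130 | Difference if they are removed |
|---|---|---|---|
| 135 / 129, 16 | 37.7% | 52.5% | 2.4 |
| 135 / 129, 20 | 40.1% | 52.0% | 2.3 |
| 140 / 134, 18 | 28.9% | 41.2% | 2.7 |
| 145 / 139, 16 | 17.4% | 28.7% | 3.3 |
| 145 / 139, 20 | 22.7% | 32.6% | 3.1 |

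Of 144 per arm, this is about 25–58 in usual care and 41–76 in coaching.

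*Model B (entry rule included).* Baseline SBP is normal with mean 135–145 and SD 15 (assumed), kept only if 130 or above. Change has SD 20 (section 7) and is independent of baseline (assumed). Mean change in usual care runs from −5 (assumed) to +10.6 (the earlier trial's usual-care figure in section 7), with coaching 6 lower. Twelve scenarios were simulated with 1,000,000 draws per arm.
- Fewest caught (baseline mean 145, change +10.6): 9.7% v 15.2%, or 14 v 22 of 144; difference if removed 4.5.
- Most caught (baseline mean 135, change −5): 34.7% v 45.3%, or 50 v 65 of 144; difference if removed 3.2.

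In every scenario of both models the coached arm loses more.

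**Step 4: set against the governing text.** Section 29 requires the 6-month visit to assess secondary outcomes. The Withdrawal section allows for leaving the trial only by the participant's decision or trial termination. Section 34 specifies intention to treat. The Form F line fits none of these.

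**The case against.** The strongest reply is that this is a template remnant that staff will see through. The forms do appear to share a template: Form B prints a health service section labelled for follow-up visits, Form F still asks whether the screening questions are complete, and some items display conditionally. A printed form does not show whether any REDCap stop sits behind the line. This stands as a limit: actual data loss is conditional on the line being followed. It does not excuse the line. The Case Report Forms section calls these forms the primary data collection instrument and lists them as designed in REDCap, and uneven compliance would still leave missingness tied to SBP.

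A second reply is that section 34 includes the most recent blood pressure in the imputation model. That helps in part. If the stop were obeyed uniformly, however, no 6-month cholesterol, glucose, BMI or LS7 total would be observed below 130, and imputation there would be extrapolation.

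A reader might infer more: that the form excludes improved participants from the primary analysis, breaks intention to treat and biases the SBP comparison. The documents do not support that. All three systolic readings and their average precede the stop, and both the Withdrawal section and section 34 point against removal. A reader might also take the MoCA note as a second stop; Form F contains no such command, so no data loss follows from it.

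**Conclusion.** The error in the form is certain; its effect depends on whether the line is followed. If it is, secondary-endpoint data after item 15A.7 are lost at the 6-month visit for everyone with average SBP below 130, and more often in the arm with lower SBP. On assumed distributions that is about 17–40% of usual care and 29–53% of coaching, or about 10–35% and 15–45% once entry at 130 or above is modelled. The resulting bias in LS7 has not been quantified and cannot be from the Protocol alone.

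The primary comparison is affected only under the further step of treating these people as removed. A true 6 mm Hg difference would then shrink to about 2.3–3.3 mm Hg in the first model and 3.2–4.5 in the second, which in most scenarios shrinks it less. These figures show what acting on the eligibility wording would cost; they do not describe what the Protocol's analysis will do.

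**What to change.** Delete the SBP-below-130 and MoCA-25-or-less eligibility messages from Form F, together with any REDCap stop logic behind them, and keep them on Form B only. If 6-month visits have already taken place, check the completed forms for items missing after 15A.7, and record how many participants are affected in each arm and why the items are missing. A sentence in section 34 saying that no randomised participant is excluded on a post-randomisation value is optional, since intention to treat is already specified there. The cost is one form edit and, if needed, a short data check; measurements not taken at 6 months cannot be fully recovered, so the edit should come before further 6-month visits.
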